Patients will be allocated to one of three groups using a web-based randomization by the SC: ketorolac, methylprednisolone, or hyaluronic acid. Group assignments will be concealed in opaque sealed envelopes with a numerical code of consecutive numbers reflecting patient enrollment. Envelopes will be stored in a secure, locked desk in the UConn orthopaedic research office and only to be opened once a patient has been determined to be eligible for study inclusion and provided informed consent.

Once informed consent is obtained, a licensed provider who is not part of the data collection (to maintain blindness) will prepare and inject the study drug. The patient will receive one of three options: 2cc of ketorolac tromethamine (15mg/cc) in 5cc of 0.5% ropivacaine hydrochloride without epinephrine, 2 cc of methylprednisolone acetate (40mg/cc) in 5cc of 0.5% ropivacaine hydrochloride without epinephrine, or Hylan G-F 20 (Synvisc-One) injection. In the US, methylprednisolone acetate is the most commonly used intra-articular steroid.¹⁷

- *Intervention: Each patient will receive one of the following interventions:*

- 1) 2cc of ketorolac *tromethamine* (15mg/cc) in 5cc of 0.5% *ropivacaine hydrochloride* without epinephrine; OR
- 2) 2 cc of methylprednisolone acetate (40mg/cc) in 5cc of 0.5% *ropivacaine hydrochloride* without epinephrine; OR
- 3) Hylan G-F 20 (*Synvisc-One*) or available hyaluronic acid.

- *Blinding:*

Both the patient and the investigators will be blinded to the treatment used until after final follow-up. Patients will not be told which drug they received. The investigators will be blinded too because the injections will be performed by a licensed provider who is not part of the data collection. Only the study coordinator will know which drug was administered and will compile the data until the study is completed.

- *Data collection:*

Patients will be asked to complete VAS, WOMAC, Oxford Knee questionnaire and Koos, Jr. Knee Survey prior to knee injection. Follow-up length is 6 months.

▪ *Sample Size and Justification:*

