A sample size calculation was performed to determine the adequate number of patients needed per group. A difference of 2 points in pain on a visual analog scale (VAS) was selected as the threshold for a meaningful between group difference. A standard deviation of 2.0 points was assumed based on previous research comparing steroid to viscosupplementation for osteoarthritis of the knee. A sample size of 20 patients per group will provide 80% power (β of 0.20) to detect a 2-point difference at an α level of 0.05 among the 3 treatment groups in an omnibus one-way ANOVA. To account for post hoc comparisons, a second calculation was carried out using a Bonferroni correction. A sample size of 25 patients per group will provide 81% power (β of 0.20) to detect a 2-point difference between each group in post hoc testing. To verify the sample size calculation, a Monte Carlo program was used to simulate 1,000 ANOVAs using these estimates with a sample size of 25 per group. This analysis resulted in greater than 90% power for the omnibus one-way ANOVA and greater than 80% for post hoc testing of between group means.

Explain on what basis it is reasonable to assume that sample size will be obtained:

Knee OA is a very common musculoskeletal condition, accounting for a significant proportion of patients presenting to orthopaedic providers.

Subject Characteristics and Justifications:

- Age: 18 years or older
- Ethnicity: No restrictions.
- Gender: No restrictions.
- Vulnerable Populations: None will be included.

Inclusion Criteria:

Patients over the age of 18 who present with 1) symptomatic knee OA and radiographic evidence of joint space narrowing and 2) are interested in knee injections for pain relief.

Exclusion Criteria:

- Patients interested in bilateral knee injections,
- Prior injections into the same knee within the past 3 months,
- Pregnant and/or lactating women,
- Inflammatory joint disease including rheumatoid or psoriatic arthritis,
- Concurrent use of anti-rheumatic drugs,
- Allergy or hypersensitivity to the study medications,
- Patients on an active pain management contract,
- Inability to make own decisions regarding the informed consent,
- Inability to read and/or understand English,
- Patients who are unable to return for follow-up or be reached by phone
- Patients with insurance that requires pre-certification for any of the study drugs.

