Describe length of subject's participation in the study including number of visits, frequency of visits and length of visits:

Patients will be in the study for 6 months. This time period will encompass their initial visit at which point they will be enrolled in the study and receive the injection as well their follow up visits. Patients will be asked to return at 3 and 6 months for evaluation and data collection. These visits are considered routine practice at our institution. Patients may also be contacted via telephone or email for follow-up if necessary. Participation will be voluntary with no financial compensation.

Methods of Data Collection and Types of Data to be Collected:

Data will consist of demographic information (age, gender, body mass index, comorbidities, etc.), as well as previous treatment modalities. The primary outcome is a visual analogue scale (VAS) for pain. Secondary measures will include the Western Ontario and McMaster Universities Osteoarthritis Index (WOMAC), length of pain relief, patient satisfaction, non-routine visits due to inadequate pain relief or complications, and cost of intervention.

Methods of Data Analysis:

Results for continuous variables will be described using means, standard deviations, medians, and/or interquartile ranges. Categorical variables will be described using counts and percentages. Numerical variables will be compared between groups using Wilcoxon's rank-sum test or Welch's two sample t-test. Categorical variables will be compared between groups using Pearson's chi-squared test or Fisher's exact test. All analyses will be done using R software (R version 3.2.3 (2015-12-10), Vienna, Austria) assuming a 5% level of significance.

5. Timetable:

Expected start date: 1/1/18

General Time Table: 1 year

Expected Completion Date: 7/31/20

6. Budget/Resources:

We will be applying for Orthopaedic Research and Education Foundation Grant during the IRB review.

7. Dissemination:

We plan to disseminate the results of our research in the form of peer reviewed publication and presentation at specialty meetings.

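### Pain and function are scored before injection, but no comparison adjusts for baseline, and the plan never says whether the follow-up score or the change is tested

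*Combined protocol and SAP*

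**What the plan says.** All places are in section 4 of the combined protocol and SAP.

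- **Data collection:** "Patients will be asked to complete VAS, WOMAC, Oxford Knee questionnaire and Koos, Jr. Knee Survey prior to knee injection". Follow-up visits are at 3 and 6 months.
- **Methods of Data Collection and Types of Data to be Collected:** "The primary outcome is a visual analogue scale (VAS) for pain". WOMAC is a secondary measure.
- **Methods of Data Analysis:** "Numerical variables will be compared between groups using Wilcoxon's rank-sum test or Welch's two sample t-test". This is the only rule given for continuous outcomes, and the significance level is 5%.
- **Sample Size and Justification:** the design targets a 2-point VAS difference in an unadjusted one-way ANOVA with post hoc comparisons. "A standard deviation of 2.0 points was assumed based on previous research comparing steroid to viscosupplementation for osteoarthritis of the knee". "To account for post hoc comparisons, a second calculation was carried out using a Bonferroni correction". The result is "A sample size of 25 patients per group will provide 81% power", which was checked by simulation: "a Monte Carlo program was used to simulate 1,000 ANOVAs using these estimates with a sample size of 25 per group".
- **Blinding:** "Only the study coordinator will know which drug was administered and will compile the data until the study is completed".

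The document nowhere mentions a baseline covariate, change from baseline, ANCOVA or a repeated-measures model.

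**The concern.** Each patient will have a baseline and a follow-up score on the primary outcome. A two-sample test of the follow-up score ignores the baseline. A two-sample test of the change fixes the baseline coefficient at 1, which is usually not the efficient value and adds noise when the correlation is low. ANCOVA estimates the coefficient from the data.

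The plan leaves two things open: which variable is tested, and whether the SD of 2.0 belongs to the follow-up score or to the change. Where the two do not match, the planned test can fall below the power stated for it. The open choice also allows both versions to be run and one to be reported.

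**Working it through.** **Inputs from Sample Size and Justification:** difference 2 points, SD 2.0, 25 per group, Bonferroni correction.

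**Assumed, not in the documents:** two-sided tests; three pairwise comparisons, so alpha = 0.05/3 = 0.0167; correlation r between baseline and follow-up from 0.1 to 0.6; the baseline SD; normal data with equal variances; 25 evaluable patients per group.

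**Step 1. The plan's own figures.** For a pairwise test with SD s, SE = s × √(2/25). With s = 2.0, SE = 0.566 and the noncentrality is 2/0.566 = 3.54. The noncentral t on 48 df gives 85.0% power, against the stated 81% (81.2% is reached at 23 per group). The omnibus F-test at 20 per group with means 0, 1, 2 gives 79.3%, against the stated 80%. The sizing is slightly conservative, not too small. At 25 per group, 81% power requires s ≤ 2.096.

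**Step 2. Reading A: 2.0 is the follow-up SD.** Let b be the baseline SD.

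- Follow-up test: s = 2.0
- Change-score test: s = √(4 + b² − 4rb)
- ANCOVA: s = 2√(1 − r²), whatever b is

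Example at r = 0.3, b = 2.0: change s = √5.6 = 2.366; ANCOVA s = 2√0.91 = 1.908.

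| r | Follow-up | Change, b = 2.0 | Change, b = 1.5 | ANCOVA |
|---|---|---|---|---|
| 0.1 | 85.0% | 56.5% | 68.9% | 85.4% |
| 0.2 | 85.0% | 62.5% | 74.5% | 86.6% |
| 0.3 | 85.0% | 69.3% | 80.4% | 88.5% |
| 0.4 | 85.0% | 76.9% | 86.5% | 91.1% |
| 0.5 | 85.0% | 85.0% | 92.1% | 94.1% |
| 0.6 | 85.0% | 92.5% | 96.5% | 97.1% |

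The change-score test is below 81% when r < (4 + b² − 4.394)/(4b), that is 0.15, 0.31, 0.45 or 0.59 for b = 1.0, 1.5, 2.0 or 2.5. Relative to the follow-up test, ANCOVA cuts the SE by 1 − √(1 − r²): 0.5% at r = 0.1, 5% at 0.3, 13% at 0.5.

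**Step 3. Reading B: 2.0 is the SD of change, with equal SDs at both times.** The follow-up SD is √(2/(1 − r)) and the ANCOVA residual SD is √(2(1 + r)).

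Example at r = 0.6: follow-up s = √5 = 2.236; ANCOVA s = √3.2 = 1.789.

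| r | Change | Follow-up | ANCOVA |
|---|---|---|---|
| 0.1 | 85.0% | 98.6% | 98.7% |
| 0.3 | 85.0% | 95.2% | 96.8% |
| 0.5 | 85.0% | 85.0% | 94.1% |
| 0.6 | 85.0% | 75.0% | 92.5% |

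The follow-up test is below 81% when r exceeds about 0.55.

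**Step 4. A floor that does not need r.** The ANCOVA residual variance is the minimum over c of Var(Y − cX), where Y is follow-up and X is baseline. It cannot exceed Var(Y), the case c = 0, or Var(Y − X), the case c = 1. If either SD is 2.0, the residual SD is at most 2.0 and power is about 85% or more. A grid of baseline SD 0.5 to 3.0 and r 0 to 0.9 under both readings has a minimum of 85.0%.

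**Step 5. Simulation.** Three-arm ANCOVA at the two worst cases (r = 0; slope 1 with SD of change 2.0) gave 85.0% in each with 40,000 trials. Repeat runs lay between 84.8% and 85.4%. Under no difference, Welch on follow-up, Welch on change and ANCOVA each rejected in 1.5% to 1.8% of trials (nominal 1.67%).

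**The case against.** The plan meets its power target on its own inputs. When the SD and the tested variable match, either unadjusted Welch test has 85.0% power against the stated 81%. The sample-size text refers to group means and never to change, so the follow-up score is the more natural reading. The low figures above come from mismatches that the documents do not say will occur. All of this stands: the trial is not shown to be underpowered, and at r = 0.1 to 0.2 the gain over the follow-up test is only 0.4 to 1.6 points.

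The 85% floor is conditional. With s = 2.0, two-sample power is 79.1% at 22 evaluable per group and 74.2% at 20, and the plan makes no allowance for dropout. Missing patients lower the power of every candidate test, so this does not favour the unadjusted ones. Pooling three arms in one model also hides a cost of about half a point for the covariate: the pooled unadjusted contrast has 85.8%. The comparison that matters here is still with the two-sample test the plan names.

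Wilcoxon and Welch tolerate skew or unequal variances better than ordinary ANCOVA, and VAS is a bounded scale. That is a fair reason to add a sensitivity analysis, not to leave baseline out. Wilcoxon itself has about 82.9% power under normality, using relative efficiency 0.955.

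Finally, the unstated choice of variable may matter more than efficiency. If follow-up and change were both tested at 5% and either reported, the simulated type I error for one pair at one visit is about 9% (r = 0.3 to 0.7). The documents do not say this will be done, but nothing in them prevents it. Naming one model closes both gaps.

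**Conclusion.** The concern holds. Baseline VAS and WOMAC are collected, no adjusted comparison is specified, and neither the tested variable nor the meaning of the SD is stated. Because treatment is randomised, this causes no bias in a test chosen in advance. The cost is precision.

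Its size depends on a correlation that the documents do not give. Under reading A, ANCOVA gains 0.4 points of pairwise power over the follow-up test at r = 0.1, 3.5 at r = 0.3 and 9.1 at r = 0.5. The omnibus test with means 0, 1, 2 moves from 88.3% to 91.2% at r = 0.3 and 95.6% at r = 0.5. The argument that does not depend on r is the floor: with 25 evaluable per group, alpha 0.05/3, normal data, equal variances and a common slope, ANCOVA has about 85% power or more under either meaning of the SD. Neither unadjusted test has that protection while both questions are open. This is a change that should be made, not a flaw that invalidates the trial.

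**What to change.** In Methods of Data Analysis, replace the two-sample tests for VAS and WOMAC with text along these lines:

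> VAS and WOMAC will each be analysed by ANCOVA of the follow-up score on treatment arm (three levels), with the pre-injection value of the same score as covariate. The omnibus comparison is the treatment F-test from this model at 5%. The three adjusted pairwise differences will be tested at 0.05/3 and reported with 98.3% confidence intervals. A rank-based or robust-standard-error version will be a sensitivity analysis.

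The omnibus and Bonferroni structure is carried over from the sample-size section. In that section, add a clause saying whether the SD of 2.0 describes follow-up scores or change.

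The model should be fixed in writing before anyone examines outcomes by arm, since the coordinator who compiles the data knows the allocation. Which visit is primary is a separate question; the same model serves 3 and 6 months.

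Cost: two or three sentences, one clause and one error degree of freedom. No new data, patients or visits are needed.

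### No missing-data method or primary visit is stated for the VAS, so a 6-month comparison would by default ignore 3-month scores of patients lost later; the main cost is power

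*Combined protocol and SAP*

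**What the plan says.** - **Outcome and visits.** VAS pain is the primary outcome (Methods of Data Collection), with no visit attached to it. On timing, the section on length of participation says: "Patients will be asked to return at 3 and 6 months for evaluation and data collection".
- **Analysis.** Methods of Data Analysis states: "Numerical variables will be compared between groups using Wilcoxon's rank-sum test or Welch's two sample t-test", "assuming a 5% level of significance". It gives no repeated-measures model, imputation, missing-data rule or analysis population.
- **Sample size.** "A difference of 2 points in pain on a visual analog scale (VAS) was selected as the threshold" for a meaningful between-group difference, and "A standard deviation of 2.0 points was assumed". For the omnibus test, "A sample size of 20 patients per group will provide 80% power". For the pairwise tests, "a second calculation was carried out using a Bonferroni correction", leading to 25 per group and a stated power of 81%. No allowance for loss is given.
- **Follow-up.** "Participation will be voluntary with no financial compensation". The same section allows telephone or email contact where needed and describes the visits as routine at the institution. The exclusion criteria rule out patients who cannot return or be reached by phone.
- **Removal.** Appendix A, item 3, lets the investigator take a patient off the trial for not completing the follow-up questionnaires.

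**The concern.** A two-sample test at 6 months has no place for a patient who has a 3-month score but no 6-month score. An ANOVA at a single visit, which the sample size section has in mind, has none either. Unless another rule is added, such a patient contributes nothing to the 6-month contrast, although the 3-month score is in hand and is informative about the missing one. The removal rule in Appendix A could add to these losses, because non-response can become removal from the trial.

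Two things are at stake. First, precision: with 25 per arm and no allowance for loss, every discarded patient counts. Second, if leaving depends on the 3-month score and the arms differ at 3 months, those who remain are no longer a fair sample of each arm, and the 6-month difference is somewhat distorted.

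**Working it through.** **1. The plan's own figures.** Inputs from Sample Size and Justification: difference 2, SD 2.0, 25 per group, alpha 0.05. Two-sided testing is assumed, and the Bonferroni level is taken as 0.05/3 = 0.0167 for three pairs of arms.
- Omnibus ANOVA, 20 per group, means 0/1/2: 79.3% (stated 80%).
- Pairwise t-test at 0.05/3: noncentrality 2 / (2 × √(1/25 + 1/25)) = 3.54, power 85.0%. With 23 per group it is 81.2%. The stated 81% at 25 per group is thus slightly conservative, and it takes all 25 as scored.

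**2. Loss scenario (assumed; the documents give no loss rate, correlation or arm means).** 3-month VAS means 3 and 5, SD 2.0. After month 3, 5% of patients with VAS below 5 leave, and 40% of the others.
- Share at or above 5: P(Z ≥ 1) = 0.159 in the better arm and 0.5 in the worse arm.
- Loss: 0.05 × 0.841 + 0.40 × 0.159 = 0.106, and 0.05 × 0.5 + 0.40 × 0.5 = 0.225 (about 11% and 22%).
- Expected completers: 25 × 0.894 = 22.4 and 25 × 0.775 = 19.4.
- Noncentrality falls from 3.54 to 1 / √(1/22.4 + 1/19.4) = 3.22 before any bias.

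**3. Bias in the completers' contrast.** Among those who stay, the 3-month mean shifts by −(0.40 − 0.05) × 2 × φ(z) / (1 − loss), where z = (5 − mean)/2.
- Better arm: −0.70 × 0.242 / 0.894 = −0.189.
- Worse arm: −0.70 × 0.399 / 0.775 = −0.360.
- The shifts differ by 0.171. With equal SDs, the 6-month bias is the correlation times this: 0.05 (correlation 0.3), 0.09 (0.5), 0.12 (0.7).
- A true difference of 2.00 is therefore estimated as 1.95, 1.91 and 1.88. The joint model estimates 2.00.
- With no 6-month difference but a 2-point difference at 3 months, the same 0.12 (correlation 0.7) appears in favour of the arm that did worse early. Type I error there is 5.4% for completers and 4.7% for the joint model.

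**4. Power by simulation, true 6-month difference 2, 25 randomised per arm** (simulation error about one point):

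| Correlation | Completers, 0.05/3 | Joint model, 0.05/3 | Completers, 0.05 | Joint model, 0.05 |
|---|---|---|---|---|
| 0.3 | 73% | 75% | 86% | 88% |
| 0.5 | 72% | 78% | 85% | 89% |
| 0.7 | 70% | 79% | 84% | 90% |

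**5. Other loss patterns (assumed), 0.05/3, 6-month means 4 and 6.**
- Loss of 20% in each arm, unrelated to the score: no bias. Completers' power is about 73%; the joint model gives 73%, 75% and 78% at correlations 0.3, 0.5 and 0.7.
- Patients who feel well leave (50% of those at 3 or below): the better arm looks worse, and the difference shrinks to 1.92-1.80.
- Heavy loss (80% of those at 7 or above), correlation 0.5: completers 1.74 with 65% power, joint model 2.00 with 77%.

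**The case against.** **Completers-only analysis is not written anywhere.** A reader might infer that the plan prescribes it. It does not: it names two tests and is silent on missing scores, and a two-sample test could follow imputation. This stands. What the text supports is that no method is stated and that these tests, used alone, leave the patient out.

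**The 6-month contrast is also not prescribed.** If the primary visit were 3 months, loss after month 3 would not touch the primary result. This stands too, and it is why the visit has to be named.

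**Retention may be good.** Phone or email follow-up, the exclusion of patients who cannot be reached, and routine visits could all keep loss low, and a VAS can be taken by phone. These measures reduce missing scores but do not say how to analyse those that remain. The loss rates used here are assumptions.

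**The bias is small.** A reader might infer that the planned test flatters the arm that did worse, or produces a false late advantage. The documents do not support that as a general statement. It needs poor responders to leave, which nothing in the plan establishes. In the moderate scenario it is at most 0.12 points against a 2-point threshold, and it barely moves the type I error. The larger biases require the heavy-loss assumption.

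**Conclusion.** The point holds as a gap with a cheap improvement. The plan states neither a primary visit nor a missing-data method for the VAS, and the tests it names make no use of 3-month scores when a 6-month score is missing.

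Under the assumed loss of about 11% and 22%, a joint model gains about 2 to 9 percentage points of pairwise power at 0.05/3, and about 2 to 6 at two-sided 5%. The gain grows with the correlation between visits and is close to nil when the correlation is low and loss is unrelated to pain. Bias is secondary: 0.05-0.12 points in that scenario, and none if loss is unrelated to the score.

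It would be wrong to conclude that the model makes good the missing allowance for loss. At 75-79% it stays below the stated 81%. These sizes rest on the assumed loss rule, 3-month means and correlations.

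**What to change.** In Methods of Data Analysis:
1. Name the primary visit for the VAS.
2. Analyse the 3- and 6-month VAS together in one likelihood-based repeated-measures model with arm, visit, arm-by-visit and an unstructured covariance. Do the same for WOMAC.
3. Include every randomised patient with at least one post-injection score. State that scores collected before any removal under Appendix A, item 3, stay in the analysis.
4. Take the arm contrasts at the primary visit from this model, with the Bonferroni correction that the sample size section already assumes.
5. Keep the two-sample test as a sensitivity analysis.

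**Cost.** A few sentences and a few lines of R, which the plan already uses; no new data, visits or patients. **Downside.** The model assumes that loss is explained by the observed scores, and patients with no post-injection score still contribute nothing. An allowance for loss in the sample size remains a separate question.

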APPENDIX A INVESTIGATOR INITIATED PROTOCOL TEMPLATE

Additional Details Pertaining to Study Design for Clinical Trials

1. For a clinical trial (e.g. a Phase I, II or III study), the use of the intervention must be fully described e.g., the treatment regimen for use of drugs, placebo, medical device etc. Also include plans for receipt of test article, storage, dispensing and reconciliation.

Intervention: Each patient will receive one of the following interventions:

- 4) 2cc of ketorolac *tromethamine* (15mg/cc) in 5cc of 0.5% *ropivacaine hydrochloride* without epinephrine; OR
- 5) 2 cc of methylprednisolone acetate (40mg/cc) in 5cc of 0.5% *ropivacaine hydrochloride* without epinephrine; OR
- 6) Hylan G-F 20 (*Synvisc-One*) or available hyaluronic acid.

Drug storage: Pyxis machine.

2. Provide a description of known adverse events due to the intervention and the plan to deal with such adverse events (e.g. does reduction, removal of device, removal from trial.):

The drug doses to be administered follow the standard of care (see pharmacy approval letter). Perhaps the main potential adverse event is infection. Patients will be counseled on signs of infection as part of the standard risks/benefits routinely performed with knee injection with instructions to call the clinic or report to the emergency room should any issues arise following the injection.

3. Describe circumstances that may lead to a subject being removed from the trial by the PI, e.g. due to failure to follow study procedures, and the process for doing so:

Meeting any of the exclusion criteria during study participation or failure/refusal to complete follow-up questionnaires.

4. Describe any stopping rules for the study:

None. All study drugs are routinely used for symptomatic knee OA.

5. Additional Comments by PI.

None.

References:

3. Bone and Joint Initiative: The Burden of Musculoskeletal Diseases in the United States. <http://www.boneandjointburden.org/2014-report/ivh12/osteoarthritis-and-allied-disorders>. Last viewed on November 12, 2007..
4. Treatment of Osteoarthritis of the Knee, 2nd Edition. American Academy of Orthopaedic Surgeons. Rosemont, IL. 2013. .

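### Appendix A item 3 allows removal of randomised, already-injected patients on grounds that can follow from poor pain relief, and nothing keeps them in follow-up or in an as-randomised comparison

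*Combined protocol and SAP*

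**What the plan says.** Appendix A, item 3 asks for the circumstances in which a subject may be "removed from the trial by the PI, e.g. due to failure to follow study procedures, and the process for doing so". The whole answer is: "Meeting any of the exclusion criteria during study participation or failure/refusal to complete follow-up questionnaires". It describes no process.

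Section 4 (Exclusion Criteria) lists eleven criteria. Four matter here:

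- "Patients on an active pain management contract"
- "Prior injections into the same knee within the past 3 months"
- "Inability to make own decisions regarding the informed consent"
- "Patients who are unable to return for follow-up or be reached by phone"

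The section on length of participation places enrolment and injection at the initial visit, with returns at 3 and 6 months and telephone or email contact if needed. VAS pain is the primary outcome, and unplanned visits for inadequate relief are a secondary measure. Methods of Data Analysis names between-group tests only.

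On blinding, section 4 says: "Both the patient and the investigators will be blinded to the treatment used until after final follow-up". It adds: "Only the study coordinator will know which drug was administered".

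**The concern.** The exclusion criteria were written for screening. Item 3 applies them again after randomisation and after the only study treatment has been given. A criterion that can be met because of poor relief then becomes a route by which the outcome decides who stays in the trial. If the arms differ in pain, removal will differ by arm even when nobody deciding knows the allocation. The remaining groups are then no longer the randomised groups.

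Three things are at stake: bias in the comparison of arms (usually towards no difference when high-pain patients are the ones removed), loss of later VAS and non-routine-visit data, and loss of power to the extent that removed patients' scores are not collected or not analysed.

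**Working it through.** **1. Which grounds can follow from the outcome**

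- *Pain management contract.* Yes. A patient can enter one after injection because pain persists.
- *Same-knee injection within 3 months.* Only if the criterion is read as covering a further injection. Read literally, the study injection itself meets it until about month 3, so every patient would qualify for removal. The criterion does not work as a post-randomisation rule.
- *Cannot be reached, or questionnaires not completed.* The missed VAS is absent in any case. What is open is whether earlier scores are kept and later contact is still attempted.
- *Loss of decision-making capacity.* This bears on the validity of consent and is a proper reason to end data collection.

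**2. Whether another section repairs this**

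None does. No section defines an analysis population, an as-randomised comparison, a missing-data rule or continued contact after removal.

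**3. The plan's own power figure**

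Inputs from Sample Size and Justification: 25 per group, difference 2, SD 2.0, Bonferroni correction (divisor not stated; taken as 3, so α = 0.05/3 = 0.0167). Noncentrality = 2 / (2.0 × √(2/25)) = 3.54 on 48 df, which gives 85.0%. The protocol states 81%, which the same formula gives at 23 per group (81.2%). The stated figure is on the cautious side and does not affect this point.

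**4. Illustration: removed patients' VAS not analysed**

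The difference and SD are the protocol's. The rest is assumed: VAS on 0–10, normal scores clipped to that range, arm means 3 v 5 or 4 v 6, and a share f of patients above a cut-off c removed.

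In each arm, let p be the proportion above c, M the arm mean and H the mean of those above c. The removed fraction is f·p, and the mean of those left is (M − f·p·H) / (1 − f·p). Attenuation is 1 − (difference left / true difference). After clipping, the true differences are 1.942 (3 v 5) and 1.968 (4 v 6).

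Worked case (4 v 6, c = 6, f = 0.5): p = 0.159 and 0.500, so 7.9% and 25.0% are removed. The difference left is 1.703, and 1 − 1.703/1.968 = 13.5%.

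Power is simulated: 25 randomised per arm, Welch test at 0.0167.

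| Means | c | f | Removed, low v high arm | Attenuation | Power |
|---|---|---|---|---|---|
| 3 v 5 | 6 | 25% | 1.7% v 7.7% | 6.4% | 80% |
| 3 v 5 | 7 | 25% | 0.6% v 4.0% | 5.1% | 82% |
| 3 v 5 | 8 | 25% | 0.2% v 1.7% | 2.9% | 83% |
| 4 v 6 | 6 | 25% | 4.0% v 12.5% | 5.1% | 78% |
| 4 v 6 | 7 | 25% | 1.7% v 7.7% | 6.2% | 80% |
| 4 v 6 | 8 | 25% | 0.6% v 4.0% | 4.9% | 82% |
| 3 v 5 | 6 | 50% | 3.3% v 15.4% | 14.5% | 72% |
| 3 v 5 | 7 | 50% | 1.1% v 7.9% | 10.7% | 78% |
| 3 v 5 | 8 | 50% | 0.3% v 3.3% | 5.9% | 82% |
| 4 v 6 | 6 | 50% | 7.9% v 25.0% | 13.5% | 67% |
| 4 v 6 | 7 | 50% | 3.3% v 15.4% | 14.0% | 72% |
| 4 v 6 | 8 | 50% | 1.1% v 7.9% | 10.2% | 78% |

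With nobody removed, the simulated power is 85%.

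**5. Illustration: removal on the 3-month VAS, only the 6-month VAS lost**

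Same scenarios, assumed correlation between visits 0.3 to 0.7. Attenuation at 6 months is 0.9% to 4.5% (f = 25%) and 1.8% to 10.2% (f = 50%).

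**6. Illustration: everyone kept, later treatment lowers the same patients' VAS by k points**

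Attenuation = k·f·(p in the higher-pain arm − p in the lower-pain arm) / true difference. For 4 v 6, c = 6, f = 0.5, k = 2: 2 × 0.5 × (0.500 − 0.159) / 1.968 = 17.3%. Over the 12 scenarios the range is 0.8% to 8.7% for k = 1 and 1.6% to 17.3% for k = 2.

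**The case against.** Several objections carry weight.

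- *The wording is permissive.* Item 3 says what may lead to removal. It does not say collected scores are discarded, and it announces no per-protocol analysis. That stands, and it makes step 5 the closer reading. But the removal rule itself is stated, and what happens to the data afterwards is left open.
- *Only one criterion of eleven is a clear outcome-related trigger.* True. The same-knee criterion counts only on one reading, and the questionnaire ground mostly describes data already missing.
- *The illustrated rates may be far too high.* No section supports them. With 5% of high-VAS patients removed, attenuation is 0.6% to 1.2%, fewer than one patient per arm of 25 is expected to be removed (at most 2.5% × 25 = 0.6), and power falls by about one percentage point at most. The effect could be negligible.
- *The PI is blinded.* This limits removal driven by knowledge of the arm, but not removal driven by outcome. The coordinator, who compiles the data, does know the arm; item 3 gives that person no role in removal, so little weight rests on this.
- *Keeping everyone can also dilute the difference.* With a 2-point later-treatment effect, retention attenuates more than removal in 2 of the 12 scenarios (4 v 6, cut-off 6: 8.7% against 5.1%, and 17.3% against 13.5%). The case for the change is therefore that it preserves the randomised groups, not that it always brings the estimate nearer to 2 points.

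**Conclusion.** The concern holds and should be fixed. The gap is certain on the text: item 3 allows removal after randomisation and treatment on at least one ground that can follow from the primary outcome, and no section keeps those patients in follow-up or in an as-randomised comparison.

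Its size cannot be derived from the documents, which give no removal rates, arm means or frequency of pain management contracts. The figures run from negligible, when removals are few, to 10.2% attenuation if half of the high-pain patients lose their 6-month score, or 14.5% if half are dropped from analysis altogether. They rest on the assumed 0–10 scale, arm means, cut-offs, removal shares and between-visit correlation. The direction, towards no difference, applies where the arms truly differ and high-pain patients are the ones removed.

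**What to change.** 1. State that the exclusion criteria decide eligibility before randomisation only.
2. Amend Appendix A item 3 so that meeting a criterion later, or missing a questionnaire, does not by itself end outcome follow-up or take the patient out of the analysis. Data collection ends when consent is withdrawn or is no longer valid, for example on loss of decision-making capacity. Clinical care decisions are unaffected.
3. State in Methods of Data Analysis that the primary comparison includes all randomised patients in their assigned group, using all available 3- and 6-month VAS.
4. Report counts and reasons for non-completion, and any later same-knee injection, by arm. A sensitivity analysis for missing or re-injected patients is optional.

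The cost is a short amendment and slightly more reporting; telephone and email contact are already allowed. The downside is that the estimate then includes the effect of any later treatment, with the dilution shown in step 6. The counts by arm let readers judge it.
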